4.2. Scientific Rationale for Study Design

The proposed trial design is considered appropriate for assessing the efficacy, safety, tolerability, PK, and immunogenicity of daxdilimab in participants with active, proliferative lupus nephritis.

4.3. Justification for Dose

Daxdilimab has been tested in a first-in-human single-ascending dose trial in adult subjects with type I IFN-mediated autoimmune diseases, and a phase 1 multiple-ascending dose (MAD) trial in adult participants with autoimmune disease with up to [REDACTED]. Daxdilimab treatment resulted in rapid and durable depletion of blood pDCs. In the MAD trial, the median percent change from Baseline in CLASI-A was -dose responsive for subjects administered [REDACTED]. Both SAD and MAD trials demonstrated acceptable safety profiles. A Phase 2 trial (Study VIB7734.P2.S1) currently enrolling participants with SLE is dosing daxdilimab at [REDACTED] followed by an open-label extension study (HZNP-DAX-204) to evaluate long-term safety and tolerability of daxdilimab up to Week 96.

In this Phase 2 trial in participants with active, proliferative LN, daxdilimab will be compared to placebo in addition to SOC background therapy. In a Phase 2 study in a similar population of proliferative LN patients evaluating anifrolumab up to [REDACTED], a Type-1 IFNAR antagonist mAb, the dosage approved for the treatment of moderate to severe SLE [REDACTED] was no different from placebo in inducing renal responses whereas an intensified dosing regimen consisting of 3 months of induction with anifrolumab [REDACTED] demonstrated a trend towards a higher proportion of patients achieving renal response at 1 year. This difference may be explained by potential IFN overexpression in the kidneys and potential loss of anifrolumab concentration due to proteinuria. One of the main mechanism of actions of pDC depletion is through suppression of the overactivated Type-1 IFN system and prompt suppression of IFN activity in the kidney is thought to be key to achieving meaningful therapeutic responses. Given the overlapping mechanism of action and potential urinary loss of daxdilimab in patients with proteinuria, we propose to initiate treatment with daxdilimab [REDACTED] SC or placebo at baseline [REDACTED] to minimize the risk of undertreatment due to an insufficient dose or urinary loss of daxdilimab. Starting at Week 8, participants on daxdilimab will receive either daxdilimab [REDACTED] or daxdilimab [REDACTED] through [REDACTED]; at [REDACTED] all participants will be assigned to a [REDACTED] based upon the renal response observed at [REDACTED] and will either receive daxdilimab or placebo every [REDACTED] through [REDACTED] (last dose administered at [REDACTED]) in addition to SOC therapy.

A 52-week treatment duration is considered sufficient to demonstrate an effect on the primary and secondary outcome measures selected for this study. The second year of the trial will provide additional data to evaluate long-term safety as well as the [REDACTED]

[REDACTED] Current nonclinical safety data, the clinical study currently enrolling participants with SLE that will dose daxdilimab for [REDACTED], and belimumab's Phase 3 trial dosing through [REDACTED] support this treatment duration.

4.4. End-of-Study Definition

A participant is considered to have completed the trial if he or she was followed through the last protocol-specified visit (ie, Week 112), regardless of the number of doses of study intervention that were received as shown in the SoA (See Section 1.3).

The end of study date is defined as the date when the last participant across all sites is assessed (ie, last subject last visit), including any additional parts in the study (eg, long-term follow-up, additional antibody testing), as applicable.

5. STUDY POPULATION

5.1. Inclusion Criteria

All participants must meet/provide all of the following criteria to be eligible for trial participation:

1. Written informed consent and any locally required authorization (eg, Health Insurance Portability and Accountability Act [HIPAA] in the United States) obtained from the participant prior to performing any protocol-related procedures, including screening evaluations.
2. Willing and able to comply with the prescribed treatment protocol and evaluations for the duration of the trial.
3. Adult men or women ≥ 18 and ≤ 80 years of age.
4. Fulfill the 2019 European League Against Rheumatism/American College of Rheumatology Classification Criteria for SLE ([Aringer et al, 2019](#)).
5. Have at least one of the following at Screening per central lab:
 - Antinuclear antibodies (ANA) $\geq 1:80$.
 - Anti-dsDNA antibodies elevated to above normal range as established by the central laboratory (ie, positive results).
 - Anti-Smith antibodies elevated to above normal (ie, positive results).
6. Diagnosis of proliferative LN based on a renal biopsy obtained within 6 months prior to signing the informed consent form (ICF) or during the Screening Period:
 - Class III (\pm class V) or class IV (\pm class V) LN according to the World Health Organization (WHO) or 2003 ISN/RPS classification (based on local evaluation of renal biopsy).
 - Note: the local biopsy report will be used to confirm participant eligibility. The submission of Screening biopsy sample (archived or fresh tissue block, slides, or digital pathology images) for adjudication is required to participate in the study.
7. Urine protein to creatinine ratio ≥ 1.5 mg/mg (113.17 mg/mmol), obtained via a 24-hour urine collection at both:
 - The start of Screening and
 - Within 14 days of expected date of Randomization. Without the results of the second sample, which will be used for stratification, participants cannot be randomized. The second sample may be collected after a minimum of 10 days after the Screening sample was obtained. The second sample may be repeated once, upon approval by the Medical Monitor (this will not be considered a re-screen). Typical turn-around time for results from central laboratory is up to 7 days. On rare occasion, an extension of the 28-day screening window is allowed

if re-collection of the sample is necessary or the results needed for Randomization are delayed.

8. Estimated glomerular filtration rate (as calculated by the MDRD formula, with screening laboratory results for serum creatinine value) ≥ 35 mL/min/1.73 m².
9. Negative serum β human chorionic gonadotropin (β -hCG) test at Screening (females of childbearing potential only).
 - Note: if the result of the serum β -hCG test is borderline or thought to be false positive, the test may be repeated during the Screening Period. The participant may continue if the repeat test is negative. Women of childbearing potential (WOCBP) (including those with an onset of menopause < 2 years prior to Screening, non-therapy-induced amenorrhea for < 12 months prior to Screening, or not surgically sterile [absence of ovaries and/or uterus]) must have negative serum and urine pregnancy tests during Screening and Randomization, respectively. Women of childbearing potential are defined as those who are not surgically sterile (ie, surgical sterilization includes bilateral salpingectomy, bilateral oophorectomy, or hysterectomy) or those who are not postmenopausal (defined as 12 months with no menses without an alternative medical cause and a follicle-stimulating hormone [FSH] within the postmenopausal range as established by the central laboratory during the Screening Period, unless on postmenopausal hormone replacement therapy)
 - WOCBP who are sexually active with a non-sterilized male partner must agree to use a highly effective method of contraception ([Table 7](#)) from signing of the informed consent and must agree to continue using such precautions through the end of the study follow-up or 6 months (approximately 5 half-lives) following the last dose of IP in the case of early withdrawal from the study, and refrain from egg retrieval/egg donation during this period. A decision about contraception after this point should be made by the participant and her regular healthcare providers.
 - Sustained abstinence is an acceptable practice; however periodic abstinence, the rhythm method, and the withdrawal method are not acceptable methods of contraception.

Table 7 Highly Effective Methods of Contraception

Physical Methods	Hormonal Methods ^a

• Intrauterine device• Intrauterine hormone-releasing system ^b• Bilateral tubal occlusion• Vasectomized partner ^c• Sexual abstinence ^d	
Combined (estrogen and progestogen-containing hormonal contraception)
 
• PO (combined pill)• Injectable• Transdermal (patch) 
Progestogen-only hormonal contraception associated with inhibition of ovulation ^e
 
• Injectable• Implantable• Intravaginal

NOTE: because mycophenolate affects the metabolism of hormonal contraceptives and may reduce their effectiveness in women receiving MMF or MPA who are using hormonal contraceptives for birth control, the participant must employ an additional contraceptive method (eg, barrier method).

PO: oral(ly).

^a Any change in hormonal birth control during the study requires use of at least two methods of highly effective contraception for at least two months.

^b This is also considered to be a hormonal method.

^c A vasectomized partner is a highly effective method of birth control provided that partner is the sole sexual partner of the woman of childbearing potential study participant and that the vasectomized partner has received medical assessment of the surgical success.

^d Sexual abstinence is considered to be a highly effective method only if defined as refraining from heterosexual intercourse during the entire period of the study and if it is the preferred and usual lifestyle of the participant.

^e Progestogen-only hormonal contraception where inhibition of ovulation is not the primary mode of action (minipill) is not accepted as a highly effective method.

10. Men who are not vasectomized must agree to use appropriate contraception so as to not impregnate a female partner of reproductive potential during the trial and continuing for at least 3 months (approximately 5 half-lives) after receipt of the last dose of daxdilimab and refrain from donating sperm during this period.

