4. STUDY DESIGN

4.1. Overall Design

This trial is a Phase 2, multicenter, double-blind, randomized, placebo-controlled, parallel-group trial to assess the efficacy and safety of daxdilimab in patients with active, proliferative lupus nephritis despite standard of care. An overview of the trial design is presented in the schematic provided in Section 1.2 and details of trial activities are provided in Section 1.3.

Approximately 210 participants will be randomized in a ratio of 1:1:1 (70 participants per group) to receive either daxdilimab [REDACTED] mg or [REDACTED] mg SC or placebo SC in addition to SOC background therapy as described below in [Table 5](#). Randomization will be stratified by:

- Pre-randomization urine protein to creatinine ratio (UPCR) < 3.0 mg/mg vs. \geq 3.0 mg/mg
- Screening eGFR < 60 mL/min/1.73m² vs. \geq 60 mL/min/1.73m²

Table 5 First Year Treatment Assignment

Group	
1	[REDACTED]
2	[REDACTED]
3	[REDACTED]

Table 6 Second Year Treatment Assignment

Group	
1	[REDACTED]
2	[REDACTED]
3	[REDACTED]

Participants may enter the study taking daily OCS at a maximum dose of 0.5 mg/kg/day of prednisone-equivalent, not to exceed 40 mg/day, and must be on a stable dose for at least 10 days prior to Randomization. In addition, participants will receive IV methylprednisolone pulse 500 mg on the day of Randomization, prior to receiving the study intervention, unless they received a methylprednisolone pulse of \geq 500 mg within 10 days prior to Randomization followed by a reducing taper of OCS for participants already taking OCS prior to entry.

For participants who are not already taking prescribed MMF prior to Randomization, the dosing of MMF will start at 500 mg twice a day (BID) for a total daily dose of 1 gm/day for the first week, increasing to 1 gm BID for a total daily dose of 2 gm/day for the second and subsequent weeks (ie, beginning on Day 8). Prior to initiation of MMF, please refer to the restricted medications section in prior and concomitant therapy criteria because of potential interaction with MMF. An equivalent dose of mycophenolic acid (MPA) may be used as an alternative to MMF.

This trial will comprise a Screening Period of approximately 4 weeks (Days -28 to -1), a Treatment Period with Randomization on Day 1 followed by treatment through [REDACTED] ([REDACTED] totaling [REDACTED]
[REDACTED]
[REDACTED]

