8.1. Efficacy Assessments

Efficacy measurements will be made at the times indicated in the Study Plan (see [Table 2](#) for procedures and assessments to be performed at Screening and [Table 3](#) and [Table 4](#) for Treatment Period and Follow-Up).

The efficacy assessments based on laboratory tests include:

- Urine protein to creatinine ratio: This consists of:
 - **24-hour UPCR:** The 24-hour UPCR will be determined via a 24-hour urine sample.

The 24-hour UPCR will be performed as follows: twice during the Screening Period, Weeks 0, 12, 24, 36, 48, 52, 64, 76, 88, 100, 104 and at ET Visits.

During the Screening Period, two samples will be required:

- Screening sample at the start of the Screening process (after the ICF is signed) and

- Stratification sample within 14 days prior to the expected day of Randomization and after a minimum of 10 days after the Screening sample was obtained. Without the results of the second sample, which will be used for stratification, participants cannot be randomized. Typical turn-around time for results from central laboratory is up to 7 days. On rare occasion, an extension of the 28-day screening window is allowed if the re-collection of the sample is necessary, or the results needed for Randomization are delayed.

Starting from Week 0 (Day 1), the 24-hour urine sample must always be collected before the administration of study intervention. The sample collected at Week 0 (Day 1) will be the baseline sample which must be provided on Day 1 prior to Randomization and administration of first dose of study intervention.

The collection of the 24-hour urine sample should start preferably in the morning of the day before the scheduled visit with the collection starting after the first void and end with the first void in the morning of the day of the visit. The urine collection may be done within 1 day prior to the visit if the urine sample can be kept refrigerated until the day of the visit.

The sample should be kept refrigerated whenever possible. If refrigeration is not possible, participants should select the coolest possible place to store their urine sample, eg, a cool room or use a portable cooler with ice/ice pack.

In the event that a participant has a medical reason which would impact the validity of the assessment of proteinuria (eg, urinary tract infection, heavy menstruation) or the sample was not collected appropriately, the collection of the sample may be completed/repeated as follows:

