8.2.2. Vital Signs

The following vital signs will be recorded at the visits specified in Section 1.3 with the participant in a seated or supine position, after having sat calmly for at least 5 minutes: systolic and diastolic blood pressure (mmHg), pulse (bpm), body temperature (°C), and respiratory rate (breaths/minute).

Weight (kg) and height (cm) will be collected to calculate the body mass index (BMI) and will be recorded at the visits specified in [1.3](#). The height will only be recorded once at the Screening Visit and the same value will be used for BMI calculation at other visits.

[figure not shown]
If deemed appropriate by the Investigator, clinically significant findings in the vital signs will exclude a participant from trial participation. Any abnormal finding related to vital signs that the Investigator considers to be clinically significant must be recorded as an AE.

8.2.3. [Electrocardiograms](#)

Twelve-lead ECGs will be performed as a safety assessment at the visits specified in [Section 1.3](#). Clinically significant findings in the ECG should exclude a participant from trial participation (as deemed appropriate by the Investigator). Any clinically significant value will be reported as an AE.

8.2.4. [Clinical Laboratory Tests](#)

Laboratory tests will be performed in a central laboratory at the visits specified in [Section 1.3](#). The tests will include urinalysis, hematology with differential, a standard chemistry panel (including liver function tests), immunology, and a serum pregnancy test (Screening) for women of childbearing potential (WOCBP). At the visits specified in [Section 1.3](#), a urine pregnancy test will be performed for WOCBP (conducted at the Investigator site). The specific tests in these panels are listed in [Table 10](#).

[REDACTED]

[REDACTED]

[REDACTED]

In case of a screening laboratory value abnormality, the test may be repeated once within the original screening time window, if the Investigator believes there is a reasonable possibility that the participant would be eligible if re-tested.

If deemed appropriate by the Investigator, clinically significant findings in clinical laboratory testing will exclude a participant from trial participation. Any clinically significant value will be reported as an AE. The laboratory results must be retained with source documents.

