4.2 Protocol Deviations

- The protocol deviations are reviewed and categorized as significant and non-significant prior to the database lock.
 - Significant protocol deviation: a protocol deviation that affects primary efficacy and safety assessments (as applicable), the safety or mental integrity of a subject, or the scientific value of the project.

- Non-significant protocol deviation: a protocol deviation that is identified but does not impact the endpoints (as applicable), the safety or mental integrity of a subject, or the scientific value of the project.

All the protocol deviations will be listed. The number and percentage of participants with significant protocol deviations by deviation reason (e.g., nonadherence to study drug, violation of select inclusion/exclusion criteria) will be summarized.

A by-participant listing will be provided for those participants who did not meet at least one eligibility (inclusion or exclusion) criterion. The listing will present the eligibility criterion (or criteria if more than one deviation) that participants did not meet and related comments, if collected.

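### Inclusion criterion 7 prints one UPCR entry limit in two units that disagree by a factor of 1.5: 1.5 mg/mg is about 169.7 mg/mmol, not 113.17 mg/mmol

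*Protocol*

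**What the plan says.** Protocol Section 5.1, criterion 7, requires a UPCR at or above "1.5 mg/mg (113.17 mg/mmol), obtained via a 24-hour urine collection at both" the start of Screening and within 14 days of the expected randomisation date. The synopsis (Section 1.1) prints the same pair of values.

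The second qualifying sample also determines the stratum: "Without the results of the second sample, which will be used for stratification, participants cannot be randomized". The stratification cut (Section 4.1) is in mg/mg only: "Pre-randomization urine protein to creatinine ratio (UPCR) < 3.0 mg/mg vs" 3.0 mg/mg or above. So are the UPCR limits for complete and partial renal response (Sections 3, 9.4.2 and 9.4.3), suboptimal response (Section 6.7.4.1.1) and discontinuation of study intervention (Section 7.1.1). We found no other mg/mmol value, and no conversion factor, in either document.

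Neither qualifying sample is the efficacy baseline. Section 8.1 states: "The sample collected at Week 0 (Day 1) will be the baseline sample", and SAP Section 4.8.1.2 uses that Day 1 sample for the model covariate.

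**The concern.** The bracket reads as a restatement of the same limit in SI units, not as a second limit. Section 5.2 prints other laboratory limits in two units, and those checked below agree. Here the SI figure looks like the equivalent of 1.0 mg/mg.

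The criterion is mandatory and applies to both samples, and Section 8 allows no waivers. Under Section 6.3 it is the investigator or designee who tells the randomisation system that the criteria are met, at about 105 centres internationally. If the two figures disagree, eligibility depends on which unit that person, or a laboratory flag, uses.

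The gap is wide on the scale of the response criteria. The bracketed value sits almost at the partial-response limit of below 1.0 mg/mg for participants with baseline UPCR of 3.0 or less. The complete-response limit of 0.5 mg/mg needs a 50% fall from 1.0 mg/mg, but a 67% fall from 1.5 mg/mg (1 − 0.5/1.5). This shows scale only. It is not an estimate of bias, because response is judged against the Day 1 sample.

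**Working it through.** **Inputs**
- Leading limit: 1.5 mg/mg (Section 5.1 and synopsis, criterion 7).
- Bracketed limit: 113.17 mg/mmol (same places).
- Molar mass of creatinine, C4H7N3O. This is not in the documents and is taken as an assumption: 4(12.011) + 7(1.008) + 3(14.007) + 15.999 = 113.12 g/mol, that is, 113.12 mg per mmol. Range examined: 113.1 to 113.2, plus 113.64 (the coarse factor 1/0.0088).

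**Formula**

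UPCR in mg/mmol = UPCR in mg/mg × molar mass of creatinine (mg/mmol).

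**Attempt to reproduce the printed figure**

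1.5 × 113.12 = 169.68 mg/mmol. The printed 113.17 is not reproduced; it is 33.3% lower (1 − 113.17/169.68).

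**Reverse conversion**

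113.17 / 113.12 = 1.0004 mg/mg.

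| Molar mass used | 1.5 mg/mg in mg/mmol | 113.17 mg/mmol in mg/mg | Ratio of the two limits |
|---|---|---|---|
| 113.10 | 169.65 | 1.0006 | 1.499 |
| 113.12 | 169.68 | 1.0004 | 1.499 |
| 113.17 | 169.76 | 1.0000 | 1.500 |
| 113.20 | 169.80 | 0.9997 | 1.500 |
| 113.64 | 170.45 | 0.9959 | 1.506 |

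**Size of the gap**

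169.68 − 113.17 = 56.51 mg/mmol, and 56.51 / 113.12 = 0.50 mg/mg. The affected band is a qualifying UPCR from 1.0 to below 1.5 mg/mg, so a participant admitted on the bracketed value could be at most one third below the leading value (0.5/1.5).

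**Could rounding explain it?**

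The pair would agree only if the molar mass were 113.17 / 1.5 = 75.4 g/mol. No rounding of a value near 113 gets there. The printed 113.17 is almost exactly the factor for 1 mg/mg. It could be a factor that was never multiplied by 1.5, or the equivalent of a 1.0 mg/mg limit; the documents do not say which.

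**Check on other two-unit limits (Section 5.2, criterion 15)**
- IgG: 600 mg/dL × 10 / 1000 = 6 g/L, as printed.
- Hemoglobin: 8 g/dL × 10 = 80 g/L, as printed.
- Glycosylated hemoglobin: 8% = 0.08, as printed.

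**The case against.** The arithmetic is not in dispute. The case on the other side is about consequence.

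- The leading value, 1.5 mg/mg, is coherent and is in the unit of every other UPCR rule. On that view only the bracketed conversion is wrong.
- Harm requires someone to use the bracket in preference to the leading value. Section 8.2.4 says "Laboratory tests will be performed in a central laboratory", and, more directly, Sections 5.1 and 8.1 refer to central laboratory results for the second sample. That result must be classed against 3.0 mg/mg before randomisation, so a mg/mg value or a correct conversion has to exist.
- Any wrong admission happens before randomisation and is unrelated to arm. Randomisation is stratified by UPCR, and the primary model adjusts for baseline 24-hour UPCR.
- SAP Section 4.2 already lists participants who fail an eligibility criterion.

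Most of this stands as a limit on the likely effect. No between-arm bias is claimed, and the number affected may be zero. But no passage states the unit in which UPCR is reported or how eligibility flags are set, so central testing lowers the risk without removing it. The eligibility listing helps only if the check behind it uses the right value.

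**Conclusion.** The contradiction is certain: criterion 7 carries two limits a factor of 1.50 apart (0.50 mg/mg, or 56.5 mg/mmol), in both places where it appears, and nothing elsewhere in the documents corrects it. The only outside input is the molar mass of creatinine, and the result holds over every value tried. Redaction or PDF reading does not explain it, because the same clean figure is printed twice.

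High confidence applies to the unit contradiction alone. The documents do not settle which limit was intended, although the position of 1.5 mg/mg and the use of mg/mg everywhere else point to it. The effect on enrolment or response rates cannot be quantified: the documents give no UPCR distribution, no response rate by baseline UPCR and no reporting unit. The point still has to be corrected, because a mandatory entry threshold is misprinted and the correction is nearly free.

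**What to change.** 1. The sponsor confirms the intended limit and reconciles the two values in the synopsis and in Section 5.1. If 1.5 mg/mg stands, replace 113.17 mg/mmol with about 169.7 mg/mmol in both places.
2. Check that laboratory flags and any eligibility check in the randomisation or data-capture system use the confirmed value.
3. Run one query for participants randomised with either qualifying UPCR from 1.0 to below 1.5 mg/mg. Review them under the provision in SAP Section 4.2: "A by-participant listing will be provided for those participants who did not meet at least one eligibility (inclusion or exclusion) criterion". Do not class them as deviations until the limit is confirmed.

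The cost is one number in two places, one check of flags and one data query. If 1.5 mg/mg stands, the sample size, the analyses and the mg/mg criterion are unchanged.
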